The overall study uses a stepped-wedge design to understand PrEP implementation at eight study sites in Yunnan, China. Each study site will go through four study periods. Sites will start with a six-month pre-baseline period, where PrEP is not offered but HIV prevention utilization data will be collected among MSM client population. HIV prevention utilization data will be captured by the PrEP M&E data system created by Yunnan CDC. Examples of indicators to be collected include number and frequency of HIV and STI tests, diagnoses, and treatment status. These metrics will be collected throughout all study periods. Each site will then have a different length of Baseline Period of standard PrEP implementation followed by a one-year Experiment Period with enhanced PrEP implementation.

The study procedures involve audio recording of research subjects. All study procedures will be performed at eight study sites by research staff who have completed human subject protection training after obtaining informed consent from participants. This study will not use previously collected biospecimens, data or records. Detailed study procedures are listed below:

Audio and/or video recording of research subjects: This study will conduct in-depth interviews with (1) MSM clients, and (2) program staff to understand their experience with PrEP implementation. Interview guides are submitted in English only as these are documents to guide the English-Chinese bilingual interviewers. Therefore, no Chinese version of the interview guide is attached. We will audio-record interviews with participants who provide permission for recording. Audio-recording is a very widely used technique in qualitative research. It allows researchers to fully engage and concentrate on the interview rather than writing notes, which may be a distraction for both the

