interviewer and the participants. Audio-recording will help researchers keep accurate records of qualitative data and capture non-verbal expressions during the interview. Informed consent will be obtained before any study procedures are initiated. During the consent process, the interviewer will ask participant's permission for audio-recording. For detailed process of obtaining consent, please see section "Informed Consent Process". After informed consent is obtained, the interviewer will announce that the interview will begin and turn on audiorecording equipment. The interviewer will begin the interview by noting the time, date, and unique ID number for the interview. S/he will proceed to conduct the interview guided by the interview guides. The interview will be in-person or remotely one-on-one and is expected to last 45 to 60 minutes. All data will be confidential and protected. Compensation of 100 Yuan (approximately USD \$16) will be provided upon completion of the interview. De-identified data will be sent to contractors external to Columbia University to support data analysis.

Study Design

B-HAPPY is a multisite randomized stepped-wedge trial to compare the effectiveness of two implementation strategy bundles: 1) Standard Implementation: comprising the strategies that the Yunnan CDC would usually use to introduce HIV prevention innovations in the absence of the proposed study; and 2) Enhanced Implementation: standard implementation enhanced by a SIC-guided approach to plan and implement PrEP. Eight sites will receive identical Standard Implementation during a six-month baseline period; additional strategies will be introduced to blocks of 2 sites in six-month increments. Importantly, the role of the SIC will shift between Baseline when

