Traditional designs—whether client-randomized or site-randomized—were not viable due to statistical power, contamination risk, and the dual focus on intervention and implementation outcomes. For instance, randomizing clients would risk contamination within sites, and randomizing sites would drastically restrict power. This

is addressed by the proposed stepped-wedge design,²⁵⁻²⁷ with all sites participating in a baseline period (Standard Implementation), experiment period (Enhanced Implementation), and post-experiment period (Observation). Blocks of sites are randomized to the *timing* of the experiment period. Because intervention condition *changes over time*, the intervention effects reflect within-block changes (e.g., between the Enhanced and Standard periods). The design is highly flexible and maximizes power, and the proposed analyses straightforwardly accommodate different data structures for client-services outcomes (Aim 1) and implementation process outcomes (Aim 2), clients that span periods, and outcomes that are both research- and site-collected.

Data structure. For Aim 1, the *client-services outcomes* are structured with repeated visits (level-1) that are nested within clients (level-2) who are nested within periods (level-3) that are nested within sites (level-4). However, for analysis, the outcomes will reflect a single status for each client (e.g., initiation of PrEP), reducing the data to a three-level structure. For Aim 2, the *implementation process outcomes* are structured with three repeated measurements (i.e., across the baseline, enhanced, and observation periods; level-1) that are nested within sites (level-2). In each case, the small number of sites will be addressed. Of note, across aims, supplementary time-to-event analyses^{28, 29} (e.g., the effect of Standard Implementation on time to client awareness) are possible by reformulating the data to client- and site-period structures. Likewise, clients will be associated with the period in which the outcome status is finalized.

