Model building, estimation, and significance testing. The nested data structures will be evaluated using mixed-effects regression models, but with 8 sites, specialized methods are required to estimate and validate the effects.^{29,30} Model estimation will utilize Bayesian Markov chain Monte Carlo (MCMC) methods.²⁷ With this approach, the results are based on a large number of replications, providing an empirically-based sampling distribution—rather than a single point estimate—for each model parameter (e.g., the effect of Enhanced Implementation). Further, the conclusions will be validated using a frequentist, fixed effects approach (i.e., dummy-coded indicators) to control for site effects.³¹ To test for within-block changes across the three periods, two dummy-coded indicators will be included to differentiate the Enhanced and Observation periods from the reference Standard period. Continuous, dichotomous, and ordered categorical outcomes will be evaluated according to Gaussian, binomial, and ordinal distributions. To evaluate the magnitude and precision of effects, 95% CIs will be computed, along with odds ratios (ORs) for non-linear outcomes. The Bayesian MCMC models will be implemented in MLwiN,²⁷ and single-level regression models will be implemented in R.³²

Evaluation of Specific Aim 1: To evaluate whether the addition of SIC-guided PrEP delivery (Enhanced Implementation) to standard health system PrEP delivery improves services outcomes, including: awareness, screening, offer, initiation, and continuation at 6 months. Although the outcomes are repeatedly monitored, each reflects a client-level status. The three-level mixed-effects regression model, with clients (level-1) within periods (level-2) within sites (level-3), will include control variables for client characteristics (e.g. age, partnership status, ethnicity [Han vs other], sexual identity) and site characteristics (e.g. staffing, collaboration history between VCT and

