STI clinics, institutional leadership, localized epidemiology), along with indicators for study periods. Additionally, to control for temporal effects—natural improvements in PrEP implementation over time—for each client, the models will control for the time of study entry using linear and quadratic polynomials for the number of months from the start of the Standard period. With a single outcome status for each client, this controls each client's outcomes for the timing of participating during the site's PrEP implementation process. The results will indicate the average within-block change from Standard to Enhanced in the log-odds of awareness, screening, offer, initiation, and continuation. Likewise, to determine whether the effects are maintained, outcomes from the Sustainment period will be compared to the Standard and Enhanced periods.

Statistical power for Aim 1. Multilevel power analysis typically assumes interventions are at the level of individuals or groups. However, here, the intervention is time-varying. As such, power for the primary client-services level outcomes was estimated using a multi-step approach recommended by Hox³³:

First, the *total sample* of observations was computed. For client-services level PrEP outcomes (ie, awareness, screening, offer, initiations, continuation), the sample size calculation reflects the size of the site client population and the availability of donated TDF/FTC (minimum of 1064 PrEP initiators). We anticipate ~2600 MSM clients per site per year and estimate ~133 PrEP initiators per site. However, this sample size is nested, introducing dependency and decreasing the level of statistical power.

Second, to penalize the total sample for nesting, the design effect formula is reorganized (i.e. $n_{\text{eff}} = n/[1+\{n_{\text{clus}}-1\}]$) to provide the effective sample size of independent observations. Using a conservative nesting effect (i.e. =0.25 for phases/sites), the

observations provide statistical power equivalent to 32 independent observations.

Despite the large number of MSM clients each year, the effective sample reaches an upper limit of 32 due to (a) the small number of sites and (b) the large cluster size per site. However, the large cluster provides high reliability for estimated level-2 effects.

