Implementation outcomes. For Aim 2, with the focus on implementation process outcomes (rather than client services outcomes), the data are structured with three periods (level-1) within sites (level-2). The outcomes include the proportion of implementation activities completed, duration of activity completion, maximum implementation stage reached, and benchmarks on the Five-80s (3 consecutive months for implementation, 6 consecutive months for sustainment). The model will include key client and site characteristics, and dummy-coded indicators to differentiate the three periods. The results will indicate the difference between Enhanced and Standard in the level of each implementation outcome. As with Aim 1, the conclusions will be validated based on single-level models with fixed-effect control variables for site differences. Likewise, with the focus on achieving implementation process benchmarks, the model

will be extended to a time-to-event framework,²⁹ testing for differences between Enhanced and Standard in the time required to achieve benchmarks (adjusted for the duration of the Standard period). With the focus on implementation process outcomes, power for this aim is inherently limited. Results will focus on estimates of 95% CIs for the effect of Enhanced Implementation.

Attrition & Missing Data. Following intention-to-treat principles, sites will be retained in research measurement independently of participation in Enhanced Implementation.³⁴ Highly successful tracking and retention protocols will minimize missing data. However, some data will inevitably be missing. To address this, assumptions will be evaluated, and informed by the results, one of several approaches will be used³⁵: i) For a small proportion of missing data with evidence of Missing at Random (MAR), the data will be analyzed using the estimation procedures described above. ii) For a non-trivial amount of missing data and evidence of MAR, multiple imputation for repeated measurements will be used.³⁶ iii) For a non-random missing data mechanism, pattern mixture models will be used to identify and control the effect of the non-random mechanism.^{37, 38}

Data Analysis

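### The Aim 2 level model has no time term, so its Enhanced-minus-Standard estimate is a before-after difference that mixes the effect of Enhanced with time

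*Combined protocol and SAP*

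**What the plan says.** The SAP's Data structure paragraph describes the Aim 2 outcomes as "structured with three repeated measurements" per site, one each for the Standard, Enhanced and Observation periods. Eight sites give 24 records. The Implementation outcomes paragraph lists four outcomes: proportion of activities completed, duration of completion, highest stage reached, and the Five-80 benchmarks. It then gives the model: "The model will include key client and site characteristics, and dummy-coded indicators to differentiate the three periods". The resulting Enhanced-Standard difference in level is to be read as the effect of Enhanced, with 95% CIs.

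The reference back to Aim 1 in that paragraph brings over one thing only, the single-level check with site fixed effects. The only time-related adjustment for Aim 2, "adjusted for the duration of the Standard period", belongs to the time-to-event extension for benchmarks.

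Under Aim 1 the SAP expects "natural improvements in PrEP implementation over time" and controls for it with linear and quadratic months at each client's study entry. A site-by-period record has no client entry date, so that control does not carry over. The general modelling paragraph lists period dummies and no time term. The design rationale says that "the intervention effects reflect within-block changes".

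**The concern.** A stepped-wedge trial separates intervention from time by comparing sites that have crossed over with sites that have not, in the same calendar interval. Collapsing each site to one record per condition discards that comparison. All sites pass through the conditions in the same order, so condition and elapsed time move together within every site, and no term in the model tells them apart.

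What is at stake is the site-level hypothesis. Study Design attaches the definition of successful implementation (all five targets met for three consecutive months) to Aim 1. The Aim 1 model, however, analyses client outcomes, of which the SAP says "each reflects a client-level status". Whether a site reaches the Five-80 benchmarks is compared between Enhanced and Standard only under Aim 2. An interval centred on effect plus trend would be reported there as the effect of Enhanced.

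**Working it through.** The plan gives no power, sample size or effect size for Aim 2, so there is no figure to reproduce. The check is on the design.

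**Inputs.** There are eight sites and three records per site (SAP). Study Procedures gives each site a "different length of Baseline Period of standard PrEP implementation followed by a one-year Experiment Period". Study Design says that "additional strategies will be introduced to blocks of 2 sites in six-month increments", after an initial six months of Standard. I read these together as four blocks that start Standard at the same time, with Standard lasting s = 6, 12, 18 or 24 months and Enhanced lasting 12. The length of Observation is not given. Trends and hazards below are illustrative, and the true effect is set to zero throughout.

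**1. Outcome averaged over each period, common linear trend of b per month.** With complete site-by-period records, the Enhanced coefficient is the mean over sites of Enhanced minus Standard.
- Midpoints are s/2 for Standard and s + 6 for Enhanced, so the gap is s/2 + 6, or 9, 12, 15 and 18 months by block.
- The mean gap is (9 + 12 + 15 + 18)/4 = 13.5 months, so the estimate is 13.5b. At 0.25 to 1 point per month that is 3.4 to 13.5 points.
- Observation minus Standard is 22.5b with a six-month Observation period (gap s/2 + 15), or 27b if all sites run to month 42.
- Site fixed effects and random intercepts (assumed ICC 0.10, 0.25, 0.50) both return 13.5b. Adding Standard duration to the random-intercept model also leaves 13.5b, because it is constant within a site.

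**2. Outcome reached within a period, constant monthly hazard h, no trend.** Standard is the mean of 1 − exp(−hs). Enhanced is 1 − exp(−12h) if scoring restarts, or the mean of 1 − exp(−h(s + 12)) if it carries over.

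| h | Standard | Restart | Carry over | Differences (points) |
|---|---|---|---|---|
| 0.02 | 25.2% | 21.3% | 41.2% | −3.9 / +15.9 |
| 0.05 | 50.1% | 45.1% | 72.6% | −4.9 / +22.5 |
| 0.10 | 72.3% | 69.9% | 91.7% | −2.5 / +19.3 |

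These differences come from unequal period lengths and the scoring rule, not from trend. Letting the hazard rise as 0.05(1 + 0.05t), with restart, gives 60.4% against 70.2%, or +9.8 points. The sign is not fixed.

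**3. Five-80 needs separate treatment.** The fifth target is six-month continuation, so it cannot be read before about month 6. Three consecutive monthly readings (6, 7, 8) put success no earlier than about month 8. A block with a six-month Standard period therefore scores zero in Standard by construction, and the table must not be applied to Five-80. With h = 0.05 but zero before month 8:
- Standard is the mean of 0, 18.1, 39.3 and 55.1, which is 28.1%.
- If Enhanced restarts with existing users still counted, it is the mean of 39.3 and three values of 45.1, which is 43.7%, or +15.5 points (from unrounded values).
- If the eight-month delay applies again, Enhanced is 1 − exp(−0.05 × 4) = 18.1%, or −10.0 points.

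**4. Can the design do better?** Yes. Adding linear calendar time to the 24 records with site fixed effects gives full rank (11 of 11 columns), and the spurious 13.5b falls to zero. Models on six-month-step records with site and step effects are also of full rank, and a common trend leaves no bias in them. Their contrast rests on steps 2, 3 and 4, where Standard and Enhanced sites coexist (6 v 2, 4 v 4 and 2 v 4 sites).

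**The case against.** **The 13.5 multiplier fits none of the four listed outcomes clearly.** This stands. Three are cumulative and one is a duration. The multiplier shows the mechanism and does not forecast the bias in any named outcome.

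**Time-to-event analyses already protect the aim.** This stands in part. The extension covers the benchmarks, and the Data structure paragraph allows optional time-to-event analyses across both aims. The SAP does not state the time origin. If time runs from the start of Standard, the baseline hazard absorbs trend. If the clock restarts at Enhanced, the adjustment for Standard duration carries only the month at which Enhanced begins. Either way, the level estimates remain as specified.

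**Aim 2 is admitted to be low-powered and is reported by CIs.** This limits the consequence. It does not re-centre the interval.

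**Six-month records suit multi-month binary benchmarks badly.** This stands. A run that crosses a step boundary would be lost, step 1 is a structural zero for Five-80, and 17 to 20 coefficients on 44 to 56 records invite separation. The fix below is shaped accordingly.

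A reader might infer that the trial cannot separate Enhanced from time at all, or that Aim 1 shares the fault. The documents support neither: the staggered crossover identifies a time effect once one is modelled, and Aim 1 includes month terms.

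**Conclusion.** The point holds for the Aim 2 level model and should be fixed. As written, its Enhanced-minus-Standard estimate is a within-site before-after difference that mixes the effect of Enhanced with the improvement over time that the SAP anticipates. Neither the site fixed-effect check nor a site-constant covariate removes this. Client characteristics may shift between periods, but they are not a time control.

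Confidence is high for the missing term and low for any size. The multiplier of 13.5 assumes the 6/12/18/24-month reading, a 12-month Enhanced period, a period-averaged outcome and a common linear trend. If Enhanced lasted six months, the multiplier would be 10.5. The documents give no trend, so a reader who concludes that Enhanced will be overstated by a known amount goes too far. For cumulative outcomes even the direction depends on period lengths and on whether implementation scores restart or carry over at Enhanced, which the SAP does not say.

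**What to change.** Make the Aim 2 effect of Enhanced time-adjusted.

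- **Measures that can be scored by calendar step.** Use site-by-step records from the dated implementation log, with site effects, calendar-time terms and condition indicators that let the effect differ by time since crossover. Report the average over the Enhanced steps. A single constant indicator is unsafe: with an effect of 0 in the first six months and 10 thereafter (true Enhanced mean 5), it returns 0.4 on 44 records (six-month Observation) or 2.2 on 56 (all sites to month 42, one Observation indicator), while separate indicators return 5.0. If Observation exceeds six months, give it one indicator per step. If the effect fades in Observation (10, 5, 0, 0), one Observation indicator gives 9.2 for the Enhanced mean; indicators by step give 5.0.
- **Maximum stage, activity completion and Five-80.** Use the dated log or monthly site data in a time-to-event model with calendar time as the time scale and condition as a time-varying covariate. Count runs across step boundaries. Treat months in which Five-80 cannot yet be met as not at risk.
- **Scoring rule.** State whether implementation scores restart or carry over at the start of Enhanced. This point does not prescribe which.
- **Three-record contrast.** Report it only as a descriptive before-after comparison.

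The work is SAP wording and a rebuilt analysis file. Completion dates are already logged through contacts every two to four weeks, and Five-80 runs already need monthly site data.

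The cost to state is precision. In residual SDs, under linear models with independent errors, the SE of the averaged Enhanced effect rises from 0.342 to 0.570 (1.7-fold; 56 records, one Observation indicator), from 0.342 to 0.682 (2.0-fold; 56 records, Observation by step) or from 0.343 to 0.684 (2.0-fold; 44 records), each against the same step records without time terms. Adding linear time to the 24 records with site fixed effects costs more: 0.50 to 1.81, or 1.81/0.50 = 3.6-fold. Serial correlation should be allowed for: with an assumed AR(1) of 0.3 to 0.7, an SE that ignores it is too small, the true SE being about 3 to 14% larger. The step model also assumes that the effect at a given time since crossover is the same in all sites. Binary outcomes at eight sites may be sparse, so intervals will be wide.

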**Yunnan-ADARC HIV Prevention Program: Developing and
Testing a Model to Implement and Sustain PrEP Delivery in China**

NCT03992274

Principal Investigator: [name], MPP, MSc

Effective: 08/31/2023 (IRB Approved)

Research Aims & Abstracts

B-HAPPY is a multisite randomized stepped-wedge study to compare the effectiveness of two PrEP implementation strategy bundles: 1) Standard Implementation: comprising the strategies that the Yunnan CDC would usually use to introduce HIV prevention innovations in the absence of the proposed study; and 2) Enhanced Implementation: standard implementation enhanced by an approach guided by the Stages of Implementation Completion (SIC) framework to plan and implement PrEP.

We **hypothesize** that adding SIC-guided implementation onto standard health system implementation of PrEP will improve outcomes and lead to greater likelihood of a) implementation success and b) sustainment. **Successful implementation** will be defined as a site achieving Five-80% targets and maintaining them three months in a row: 1) Awareness of PrEP among 80% of MSM clients; 2) PrEP eligibility assessment for 80% of MSM clients; 3) PrEP linkage for 80% of MSM clients who wish to start and are medically-eligible; 4) PrEP initiation for 80% of MSM who linked to PrEP services; and 5) six-month PrEP continuation for 80% of those who remain PrEP-eligible.

Sustainment will be defined as achieving the Five-80s continuously over 6-months.

To examine the implementation process and efficiency of the Enhanced versus Standard implementation approaches we will use SIC and COINS tools to monitor sites for implementation process and resource use. Outcomes will include proportion of implementation activities completed, duration of each implementation phase, and cost and resource allocation for completion of each implementation phase. Based on robust studies that assess implementation using the SIC, we **hypothesize** that time and

resources spent in Pre-Implementation will be associated with higher odds of successful implementation and sustainment

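### The time-to-benchmark comparison states no time origin, and its only named adjustment, Standard duration, cannot remove the head start that Enhanced has from time since PrEP start

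*Combined protocol and SAP*

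**What the plan says.** The Implementation outcomes paragraph of the Statistical Analysis Plan sets out the Aim 2 layout: "the data are structured with three periods (level-1) within sites (level-2". Its model terms are client and site characteristics and "dummy-coded indicators to differentiate the three periods". It then extends this model to time-to-event, "testing for differences between Enhanced and Standard in the time required to achieve benchmarks (adjusted for the duration of the Standard period". No time origin is given for either record, and no rule for a site that reached the benchmark during Standard.

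The Data structure paragraph says, for both aims, that supplementary time-to-event analyses "are possible by reformulating the data to client- and site-period structures".

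On timing, Study Design says "Eight sites will receive identical Standard Implementation during a six-month baseline period" and "additional strategies will be introduced to blocks of 2 sites in six-month increments"; Study Procedures says "Each site will then have a different length of Baseline Period of standard PrEP implementation", followed by one year of Enhanced. Research Aims & Abstracts makes the fifth target "six-month PrEP continuation for 80% of those who remain PrEP-eligible". The benchmark is three consecutive months at all five targets for implementation and six for sustainment.

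The Aim 1 model, by contrast, includes linear and quadratic terms for months since the Standard period began, because implementation is expected to improve with time. No such term is named for Aim 2.

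**The concern.** A comparison of time under Standard with time under Enhanced is informative only if both times start from comparable states. They do not. Standard starts with no PrEP users, so nobody can yet have continued for six months. Enhanced starts after 6 to 24 months of PrEP delivery, when that target is already measurable. If each period has its own clock, Enhanced looks faster even when it does nothing.

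Aim 2 asks about the time each strategy requires, and the study's product is an implementation blueprint. A biased contrast here could credit Enhanced with speed that comes only from following Standard. The randomized step times, which could separate the two, are not used by the stated adjustment.

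**Working it through.** The plan gives no error rate, power or event count for this analysis, so there is no figure to reproduce.

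**Inputs from the documents.** Eight sites in four blocks of two. Six months of Standard plus six-month increments gives Standard lengths of 6, 12, 18 and 24 months. Enhanced lasts 12 months. The benchmark is a run of three or six months.

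**Earliest possible attainment.** Users who start in PrEP month 1 complete six months at the end of month 6, so continuation is first measurable in month 6 or 7.
- Three-month run in Standard: months 6–8 or 7–9, so it finishes at month 8 or 9 at the earliest. It cannot finish in a 6-month Standard period.
- Three-month run on a clock restarted at Enhanced: months 1–3, so it can finish at month 3. This holds even in the first block, where Enhanced month 1 is PrEP month 7.

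Equal times are therefore not what no Enhanced effect predicts. This step needs no simulation.

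**The adjustment.** Standard duration takes the same value on both records of a site. A covariate that is constant within a site cannot absorb a difference between that site's two records.

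**Size.** Assumptions: no Enhanced effect and no time trend; a site meets all five targets in a given month with the median probability shown (site SD 0.7 on the logit scale, months independent within site); no attainment before PrEP month 7. Test: Cox likelihood ratio, two-sided 5%, adjusted for Standard duration. The 5% level is inferred from the planned 95% CIs. Each setting used a few hundred trials; with 400, the simulation error is at most √(0.5 × 0.5/400) = 0.025.

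| Three-month benchmark, monthly attainment | Clock restarted: Enhanced falsely faster | Both times from PrEP start, no delayed entry: Enhanced falsely slower |
|---|---|---|
| 0.2–0.3 | 3–9% | not tabulated |
| 0.5 | 24% | 42% |
| 0.7 | 50% | 74% |
| 0.85 | 85% | 93% |

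The last column follows from the arithmetic. Without delayed entry the Enhanced time includes the whole Standard period, so it is at least 6 + 3 = 9 months in the first block and 24 + 3 = 27 in the last.

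For the six-month benchmark, the restarted clock gives about 0–33% over the same attainment range. A repeat of this model gave 40% at 0.85, so the top end is a third or somewhat more.

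**What drives it.**
- With no continuation delay and no trend, the restarted clock gives 0–2%.
- Barring sites that succeeded in Standard from re-entering still leaves 16%, 34% and 76% at attainment 0.5, 0.7 and 0.85.
- Setting every Standard period to 18 months or longer still leaves 17–81% over attainment 0.5–0.85 in separate runs.

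**Other models.** With months correlated within site and no trend, the rate is 22–69%; with improvement over time, 57–100%; when attainment is rare (about 10% or fewer of sites in Standard), 0.3–18%.

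**The alternative.** One clock from PrEP start, first attainment only and Enhanced time-varying gives 0–4% in each direction in the same settings.

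**The case against.** The strongest reply is that the plan does not say the clock restarts. That is correct. The site-period layout named under Data structure also fits one running clock with Enhanced switching on, which is the remedy proposed here. A reader might infer that the plan commits to a restart; the documents do not support that. The restart is the natural reading of a three-periods-within-sites layout, and the Standard-duration adjustment would have little purpose on a single clock. But both ways of giving each period its own time are biased, in opposite directions, and the one adjustment that is named cures neither. So the problem is more than a missing detail.

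A reader might also treat a high false-positive rate as a property of the plan. It is not: the rate depends on attainment, which the documents do not give, and Study Design calls the targets ambitious. At low attainment the inflation is small or absent.

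It is tempting, too, to blame sites that had already met the benchmark. The results above show that prior success is not the driver; the continuation delay is, and improvement over time adds to it.

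Finally, the plan calls time-to-event analyses supplementary, concedes limited power for Aim 2 and puts the weight on 95% CIs. Aim 2 also measures time through duration of activity completion, so this is not its only answer on time. These points limit the consequence. They do not excuse the bias, because a biased estimate gives a misplaced interval.

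**Conclusion.** The concern holds in conditional form. As specified, the comparison has no stated origin and an adjustment that cannot do its job. If the clock restarts at Enhanced, the contrast is confounded with time since PrEP start and favours Enhanced. If both times run from PrEP start without delayed entry, it favours Standard.

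The direction follows from the continuation target and the step schedule alone. The size rests on assumed attainment, site variation and independence of months. With no effect and no trend, the restarted clock gives about 3–9% false claims for Enhanced at attainment 0.2–0.3 and about 24–85% at 0.5–0.85 on the three-month benchmark, against a nominal 2.5% in that direction. The improvement over time that the Aim 1 section expects would generally add to this. The analysis should be respecified, with the urgency that suits a supplementary one.

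**What to change.** Replace the Standard-duration adjustment in the Implementation outcomes paragraph with text along these lines:

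*Time to first attainment of each benchmark will be analysed with one record per site on a single clock: months since PrEP start, or calendar month if PrEP starts differ between sites. Enhanced is a time-varying indicator that switches on at the randomized step, so sites in Enhanced are compared with sites still in Standard in the same month. A site leaves the risk set at first attainment. Every first attainment counts in the month it occurs, under the condition then in force. A sensitivity analysis will address runs that straddle the switch to Enhanced.*

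Runs begun in Standard should not be excluded by default. That would make Enhanced events impossible in Enhanced months 1–2 (1–5 for the six-month benchmark) while Standard sites could still have events, an asymmetry against Enhanced. The text should also say whether follow-up is censored at the end of the one-year Enhanced period, as the check assumed.

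The cost is SAP wording and a recoded data set, with no new data. The price is precision: at most eight events, and no information once no site remains in Standard. Power is low when most sites attain early. For a monthly odds ratio of 3.3 (borrowed from the Aim 1 power section for scale only), three-month power was about 27%, 15% and 3% at attainment 0.5, 0.7 and 0.85. The result should be reported as an estimate with a wide 95% CI, and a null result should not be read as evidence of equal speed.
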